## 1. OBJECTIVES

The objective of this prospective single-arm trial is to evaluate if the Gardasil® 9 HPV vaccine induces and sustains an adequate immune response at 12-months post-transplantation among 18-49 year old kidney transplant recipients when  $\geq 1$  doses of the vaccine are administered prior to transplantation.

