## **Exploratory Endpoints**

- 1) HPV vaccine-type-specific seroconversion rates at 12-months post-transplantation stratified by:
  - a) time elapsed between last vaccine dose and the transplant procedure;
  - b) variations in doses and types of post-transplant immunosuppressant medications; and interactions with type of transplant surgery (living donor/deceased donor);
  - c) differences in Human Leukocyte Antigen (HLA) histocompatibility between donor and recipient;
  - d) differences in biological sex (i.e. male vs. female) of the transplant recipient.
- 2) Stability of HPV vaccine-type-specific geometric mean titers (GMT) at 6- and 12-months post-transplantation and rise in HPV vaccine-type-specific GMT at the 13-month post-transplant visit.
- 3) Vaccine safety profile and allograft rejection/opportunistic infections stratified by number of vaccine doses and time between the last vaccine dose and the transplant procedure.
- 4) HPV detection in samples from the cervix/vagina, and oral cavity at baseline (pre-vaccination) and at 6- and 12-months post-vaccination, overall and by number of vaccine doses (1, 2, or 3), sexual behavior, type-specific seroconversion rates, and time elapsed between the last vaccine dose and the transplant procedure.

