### Exploratory Endpoints:

- 1) Descriptive statistics, such as probabilities and exact 95% confidence intervals, will be used to summarize probability of seroconversion at 12 months post-transplant for the following groups:
  - a) time elapsed between last vaccine dose and the transplant procedure, e.g. <3 months vs. >3 months. Different groupings will be considered based on observed (e.g. median) and clinical considerations. Time will be summarized using descriptive statistics, e.g. median, interquartile range, or range; groups defined by dosing and types of post-transplant immunosuppressant medications, as well as;
  - b) type of transplant surgery (living donor/deceased donor);
  - c) differences in Human Leukocyte Antigen (HLA) histocompatibility between donor and recipient:
  - d) differences by biological sex (i.e., male vs. female) of the transplant recipient.
- 2) Stability of HPV vaccine-type-specific geometric mean titers (GMT) at 6 and 12- months post-transplantation, and rise in HPV vaccine-type-specific GMT at the 13 month post-transplant visit.
  - a) Stability will be evaluated in relation to changes in the type-specific GMTs between the two post-transplant time points (6- and 12-months post-transplant) and reported as follows: (i) decrease: more than 2-fold decrease, (ii) stable: within 2-fold change, and (iii) increase: greater than 2-fold increase.
  - b) The magnitude of increase in type-specific GMTs at the 13-month post-transplant visit (i.e., 1 month after the booster dose) will be described in relation to the type-specific GMTs at the other post-transplant visits (6 and 12-months post -transplant). Patterns over time will also be explored using graphical techniques.
  - c) Stability, and post-booster dose increase in type-specific GMTs will also be described in relation to the number of vaccine doses (1, 2 or 3) received in the pre-transplant period.
- 3) Vaccine safety profile and allograft rejection/opportunistic infections will be summarized using descriptive statistics, stratified by number of vaccine doses and time between the last vaccine dose and the transplant procedure.
- 4) HPV detection in samples from the anogenital, and oral cavity specimens at baseline (prevaccination) and at 6- and 12-months post-vaccination, overall and by number of vaccine

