# 13.6 Reporting and Exclusions

We anticipate some drop-outs due to transplantation complications, health deterioration, or death. The drop-out rate is expected to be 20%, resulting in a final sample of 24-28 participants who complete the study.

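### The 6-to-12-month GMT change is classed as stable from the point estimate alone, with no confidence interval, so the class does not show that titres held, least of all within dose groups

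*Combined protocol and SAP*

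**What the plan says.** Section 8.2 lists as an exploratory endpoint "Stability of HPV vaccine-type-specific geometric mean titers (GMT) at 6- and 12-months post-transplantation". Section 13.5, item 2(a), gives the method: "Stability will be evaluated in relation to changes in the type-specific GMTs between the two post-transplant time points", reported as "i) decrease: more than 2-fold decrease, (ii) stable: within 2-fold change, and (iii) increase: greater than 2-fold increase". Item 2(b) describes the post-booster rise and adds graphs over time. Item 2(c) carries the description into dose groups: "Stability, and post-booster dose increase in type-specific GMTs will also be described in relation to the number of vaccine doses (1, 2 or 3").

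Sections 13.4 and 13.5 give no interval, SD, test or minimum n for any GMT. Intervals are specified elsewhere. The primary seroconversion rate has Clopper-Pearson 95% limits (13.4), the secondary endpoint has exact 95% limits at 6 and 12 months by dose (13.5), and exploratory item 1 says "Descriptive statistics, such as probabilities and exact 95% confidence intervals, will be used to summarize probability of seroconversion at 12 months post-transplant". Section 13.6 expects dropout of 20%, "resulting in a final sample of 24-28 participants who complete the study".

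**The concern.** A class named 'stable' with a numerical limit will be read as a finding about durability. Under item 2(a) it is also what a noisy estimate gets unless it happens to be extreme: a GMT change estimated from four people gets the same class as one estimated from 24. Item 2 is the only planned classification of how titres move between 6 and 12 months. Seroconversion cannot stand in for it, because it is a threshold endpoint and a titre can fall several-fold while staying above the assay cut-off.

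Section 13.4 says that the revised plan should allow comparison with other studies and supply preliminary data for larger ones. A bare class serves neither purpose; a ratio with its interval serves both. Dose groups are the weak spot, since 24 to 28 people are divided among three of them. Appendix G may reduce the numbers further: it makes the 6-month visit optional and lets the 12-month visit move by up to 6 months either way, so fewer than 24 participants may have both titres.

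**Working it through.** **The plan's own figures.** None is stated for the GMT rule. The nearest are the one-sided 95% upper limits for seroconversion in Table 3 at n=24 and n=28. They reproduce as Clopper-Pearson limits to within 0.0001 in all ten cells (for example n=24, P=0.65: 0.8087 against 0.8088).

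**Inputs.**
- Band: ratio 0.5 to 2.0, or -1 to +1 on the log2 scale (13.5, item 2(a)).
- Total n: 24 to 28 (13.6).
- Stratum sizes: not given. An equal three-way split of 24 gives 8; n=4 stands for a small stratum. Both are assumptions.
- SD of the within-person log2 change: not given. Assumed 0.75, 1.0 and 1.5, with normal log titres.

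**Probability of the class 'stable' as written.** With true log2 change μ and se = SD/√n,

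P(stable) = Φ((1 - μ)/se) - Φ((-1 - μ)/se).

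For a true 2.5-fold fall, μ = -log2(2.5) = -1.322. The first term is practically 1, so P ≈ 1 - Φ(0.322/se). At n=24 and SD 1.0, se = 0.204, 0.322/0.204 = 1.58 and P = 0.06.

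| n | SD 0.75 | SD 1.0 | SD 1.5 |
|---|---|---|---|
| 24 | 0.02 | 0.06 | 0.15 |
| 8 | 0.11 | 0.18 | 0.27 |
| 4 | 0.20 | 0.26 | 0.33 |

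For a true 3-fold fall at n=24 the largest value is 1 - Φ(0.585/0.306) = 0.03. A wider assumption, SD 1.5 on the natural-log scale (1.5/0.693 = 2.16 in log2 units), gives 0.23 at n=24 and 0.34 at n=8 for the 2.5-fold fall.

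**What the class can conceal.** Take an observed ratio of 0.60, which is 'stable' under the rule, with SD 1.0. The 90% interval is 2^(log2 0.60 ± t × SD/√n), and log2 0.60 = -0.737.
- n=4: half-width 2.353 × 0.500 = 1.177; interval 0.27 to 1.36. The lower end is a loss of 1/0.27 = 3.7-fold.
- n=8: 1.895 × 0.354 = 0.670; interval 0.38 to 0.95.
- n=24: 1.714 × 0.204 = 0.350; interval 0.47 to 0.76.

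**Effect of requiring the interval inside the band before stability is called shown.** Simulated with normal log2 changes and a t-interval, 400,000 draws per cell. At a true 2-fold fall the condition is met at most 5% of the time. For an unchanged titre it is met as follows:

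| n | SD 0.75 | SD 1.0 | SD 1.5 |
|---|---|---|---|
| 24 | 1.00 | 1.00 | 0.87 |
| 8 | 0.92 | 0.63 | 0.17 |
| 4 | 0.42 | 0.20 | 0.05 |

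At the wider natural-log SD of 1.5, the n=24 value falls to 0.42.

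**Effect of also requiring the whole interval beyond 2-fold before a decrease is reported.** For a true 2.5-fold fall at n=24, reporting of a decrease drops from 98/94/85% under the written rule to about 65/46/27% (SD 0.75/1.0/1.5). At n=8 it drops from 89/82/73% to 29/21/14%.

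**The case against.** The strongest reply is that item 2 is exploratory and descriptive. It has no hypothesis, alpha or success criterion, and Section 13.4 says that version 3.11 gave up pre-specified comparisons. That stands as far as it goes. A reader might infer that the plan draws a formal equivalence conclusion; the documents never call it one. But a descriptive plan still needs to show precision, and this one does so for seroconversion.

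A reader might also infer a 50% error rate, because a true 2-fold fall is classed as stable about half the time at any n. That is arithmetically right, but any cut-off applied to a point estimate behaves this way at its own limit, and a change of exactly 2-fold is not a decrease under the plan's definition. The informative figures are those for falls beyond the band.

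A third tempting inference is that the objective, that the vaccine "induces and sustains an adequate immune response at 12-months post-transplantation", rests on this rule. It rests mainly on 12-month seroconversion, reported with exact intervals, and the secondary endpoint covers 6 and 12 months by dose in the same way.

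Finally, the sizes depend on SDs and stratum sizes that the documents do not give. That is true. The absence of an interval does not depend on them.

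**Conclusion.** The point holds as a reporting weakness in an exploratory endpoint. As written, 'stable' describes where the observed ratio fell and does not show that titres held. Under the assumed log2 SDs of 0.75 to 1.5, a true 2.5-fold fall is classed as stable about 2 to 15% of the time in a cohort of 24, 11 to 27% in a stratum of 8 and 20 to 33% in a stratum of 4. The full cohort is fairly well protected against larger falls, so the weakness lies mostly in item 2(c). The figures rest on the assumed SDs, the assumed stratum sizes, log-normal titres and complete pairs. No primary or secondary conclusion changes. It is worth correcting because the correction is cheap and improves what the trial can say about durability.

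**What to change.** In Section 13.5, items 2(a) and 2(c):
- Report, for each HPV type, the paired 12-month/6-month geometric mean ratio with its 90% t-interval on the log scale and the number of participants with both titres, overall and by dose group.
- Keep the 2-fold bands, described as categories of the point estimate.
- State that titres are shown to be stable only when the whole interval lies within 0.5 to 2.0.
- Do not require the whole interval to lie beyond 2-fold before a decrease or increase is reported. As shown above, that would turn many real losses into inconclusive results, even in the full cohort.

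The cost is a few sentences and a routine interval on data already collected. The downside is that few dose groups will support a statement of stability. The full cohort usually can if titres are truly unchanged and the SD is in the assumed range, but less often if the SD is larger or many 6-month visits are missed.

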**Pre-transplant work-up and vaccinations**: The timing of vaccination in relation to the transplant surgery are considered in relation to several factors. The time available between enrollment and the transplant surgery and the feasibility of study visits in the pre-transplant period will vary by type of surgery (living donor versus deceased donor transplant). Further, the possibility of integrating with the schedule for pre-transplant clinical work-up or visiting for a study-specific purpose alone will vary by the clinical condition of the potential participants and the institutional transplant center visit requirements for every clinic site. All enrolled participants are expected to receive at least 1 dose of the vaccine prior to transplant surgery with at least 30-days between the first dose and transplant surgery. There are specific CDC recommendations about the minimum time between doses which will affect when the second and third doses are administered (see section 5.1). Other than requiring adherence to these minimum intervals (within +/- 2 weeks), the protocol will not mandate specific time windows for receiving the vaccine, considering challenges of accrual/retention in the study. Transplant candidates are typically burdened with ongoing pre-transplant clinical issues and have non-uniform follow-up visit schedules. Study staff will attempt to maximize opportunities for coordinating study-related visits on the same day as scheduled transplant-related/clinical care-related visits. However, the timing of transplant surgery is dependent on a range of factors, several of which are unpredictable at the time of study enrollment. Therefore, not all participants in the study may be able to receive all three doses of the vaccine prior to transplant. In fact, the second and third doses can be administered in the pre-transplant period or be administered at or after 12-months post-transplant.

With a few exceptions (see below), most participants will undergo the following study visits based on the number of doses that might be able to be administered prior to surgery:

	Participant is able to complete only 1 dose prior to surgery	Participant is able to complete 2 doses prior to surgery	Participant is able to complete 3 doses prior to surgery	
Consent and Screening Visit	Consent	Consent	Consent	
Pre-Transplant Vaccine Visit 1	Vaccine #1 & specimen collection	Vaccine #1 & specimen collection	Vaccine #1 & specimen collection	

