# 5.1 Dose Regimen and Dose Groups

- Agent: Gardasil® 9 nonavalent HPV vaccine
- Dose and regimen for agent: 0.5 mL single-dose for intramuscular administration
- Duration for agent: Gardasil® 9 must be administered according to the following requirements:
  - o Dose 1:  $\ge$  30 days prior to transplant
  - o Dose 2:  $\geq$  30 days after Dose 1
  - Dose 3:  $\geq$ 5 months after Dose 1 AND  $\geq$  3 months after Dose 2
- All participants will be offered the entire 3-dose series. Due to differences in the timing of
  transplant surgery, the feasibility of additional study-related visits prior to transplant surgery, and
  the possibility that transplant surgery will not occur within 12 months of enrollment, there are six
  different dosing schedules, outlined in Table 2 below.

Table 2. Dose Regimens

	Participant is able to complete only 1 dose prior to surgery	Participant is able to complete 2 doses prior to surgery	Participant is able to complete 3 doses prior to surgery	Participant completes 1 dose, but transplant does not occur within 12 months of enrollment	Participant completes 2 doses, but transplant does not occur within 12 months of enrollment	Participant completes 3 doses, but transplant does not occur within 12 months of enrollment
Dose 1		≥	30 days prior to	Transplant Surge	гу	
Dose 2	12 months (±2 weeks) after Transplant Surgery  12 months ≥30 days after Dose 1		≥30 days after Dose 1	12 months (±2 weeks) after Dose 1	≥30 days after Dose 1	≥30 days after Dose 1
Dose 3	3 months (+4 weeks) after Dose 2	12 months (±2 weeks) after Transplant Surgery	≥5 months after Dose 1 AND ≥3 months after Dose 2	3 months (+4 weeks) after Dose 2	12 months (±2 weeks) after Dose 2	≥5 months after Dose 1 AND ≥3 months after Dose 2

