#### **5.6** Dose Modification

No dose modifications are planned. The study agent will be stopped in the event of an AE  $\geq$  grade 3 considered possibly, probably, or definitely related to the study agent. The second or third dose of Gardasil® 9 will not be administered to participants who experienced symptoms indicative of hypersensitivity after the first and/or second dose(s).

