## 8.3 Off-Agent Criteria

Participants may stop taking study agent for the following reasons: completed the protocol-prescribed intervention, AE or serious adverse event (SAE), inadequate agent supply, noncompliance, or medical contraindications. Participants will continue to be followed, if possible, for safety reasons (e.g., telephone contact 24-72 hours after receiving each vaccine dose to ask about potential side effects of the immunization; and a follow-up call on day  $7 \pm 2$  days to assess resolution if the participant reports adverse symptoms). Participants who receive one or two doses of the vaccine in the pre-transplant period and go off-agent due to any reason stated above will be offered the post-transplant study visits at 6-months, 12-months and 13-months to collect endpoint data according to the schedule of events, even though the clinical and/or logistical situation that led to the participant going 'off-agent' might not permit giving the remaining vaccine doses at any of these visits.

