#### 11.1 Adverse Events

#### 11.1.1 Reportable AEs

All AEs that occur after the informed consent is signed and baseline assessments are completed (including run-in) must be recorded on the AE CRF (paper and/or electronic) whether or not related to study agent.

For all unsolicited AEs not meeting the criteria for "Serious Adverse Events", the following caveats will apply:

- a. **AEs in the immediate (up to 14 days) post-vaccination periods:** All unsolicited AEs, including anticipated and unanticipated clinical events, clinically significant laboratory abnormalities, and vaccine-related injection site local reactions (e.g., pain, swelling, erythema, pruritus, induration, warmth, etc.) and vaccine-related systemic side-effects (e.g., headache, oral temperature ≥100 degrees F, nausea, fatigue, dizziness, allergic events, bronchospasm, etc.) will be collected for up to 14 days following vaccine administration (1st, 2nd, and 3rd dose) and reported on AE CRFs.
  - i. Note that clinically significant laboratory abnormalities that *pre-dated* vaccine administration and *remain unchanged* (as per the Site Principal Investigator's judgment) after vaccine-administration should not be reported as AEs

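### Exploratory item 3 tabulates vaccine reactions by number of doses, a count that depends partly on the reactions and on unequal exposure; the main table should be per injection

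*Combined protocol and SAP*

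**What the plan says.** Section 13.5, exploratory item 3, covers the vaccine safety profile together with allograft rejection and opportunistic infections. These "will be summarized using descriptive statistics, stratified by number of vaccine doses and time between the last vaccine dose and the transplant procedure". The item gives no unit of analysis and no denominator, and does not say which doses are counted. The secondary endpoint and item 2c in the same section both count doses given before transplant; item 3 lacks that qualifier.

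Other sections decide what the dose count means:

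- Section 5.6: "The study agent will be stopped in the event of an AE" of at least "grade 3 considered possibly, probably, or definitely related to the study agent". It also withholds the second or third dose after hypersensitivity symptoms.
- Section 8.3 lists the reasons for coming off agent: "completed the protocol-prescribed intervention, AE or serious adverse event (SAE), inadequate agent supply, noncompliance, or medical contraindications".
- Section 3, on the timing of surgery: "Therefore, not all participants in the study may be able to receive all three doses of the vaccine prior to transplant".
- Section 5.1: "All participants will be offered the entire 3-dose series". Its Table 2 places the outstanding doses about 12 months or more after transplant for those who had one or two beforehand.
- Section 11.1.1 says that unsolicited events, including local and systemic reactions, "will be collected for up to 14 days following vaccine administration", and names the 1st, 2nd and 3rd doses.
- Section 13.7 makes every participant evaluable for toxicity from the first dose.

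**The concern.** A stratifier should not be determined by the outcome that it stratifies. Here it partly is: a participant with a qualifying event after dose 1 stays at one dose by rule, and one with a qualifying event after dose 2 stays at two. Event rates by doses received will therefore differ even if each injection carries the same risk.

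Reactions that do not stop dosing pull the other way, since a participant observed over three 14-day windows has more chances to report one than a participant observed over one.

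The second stratifier does not suit reactions either. The interval from last dose to transplant says nothing about a reaction to an earlier dose. It does not exist for a participant who is never transplanted, and it is negative if the last dose is taken to be one given after surgery.

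What is at stake is the only safety analysis that Section 13 specifies. A reader could see a dose pattern that the layout produced, and could not see how well injections were tolerated before and after transplant.

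**Working it through.** The plan gives no figure on this point, so there is none to reproduce. The check asks what the table would show if dose number had no effect on risk.

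**Inputs.** The stopping rule is from 5.6 and the 14-day windows from 11.1.1. For scale, n = 28 is the upper end of the 24 to 28 evaluable participants in 13.3; the toxicity set is larger. Two inputs are assumptions, because the documents do not give them:

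- q, the risk of a dose-stopping event per dose, equal at every dose: 0.5% to 10%.
- w1, w2, w3, the shares who would reach 1, 2 or 3 doses if no such event occurred: 33/33/33, 50/30/20 or 70/20/10 for a pre-transplant count; 10/10/80 or 5/5/90 for a total count.

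**Dose-stopping events, by doses received.**

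- One dose: q / [w1 + (w2 + w3)q]
- Two doses: (w2 + w3)(1 − q)q / [w2(1 − q) + w3(1 − q)q]
- Three doses: q

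At q = 2%, pre-transplant 50/30/20: one dose 0.02 / (0.50 + 0.50 × 0.02) = 0.02 / 0.51 = 3.9%; two doses 0.0098 / 0.2979 = 3.3%.

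At q = 2%, total 10/10/80: one dose 0.02 / (0.10 + 0.90 × 0.02) = 0.02 / 0.118 = 16.9%; two doses 0.01764 / 0.11368 = 15.5%.

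| Count (assumed shares), q = 2% | 1 dose | 2 doses | 3 doses | Ratio 1 : 3 |
|---|---|---|---|---|
| Pre-transplant 33/33/33 | 5.8% | 3.9% | 2.0% | 2.9 |
| Pre-transplant 50/30/20 | 3.9% | 3.3% | 2.0% | 2.0 |
| Pre-transplant 70/20/10 | 2.8% | 3.0% | 2.0% | 1.4 |
| Total 10/10/80 | 16.9% | 15.5% | 2.0% | 8.5 |
| Total 5/5/90 | 29.0% | 27.9% | 2.0% | 14.5 |

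Over q from 0.5% to 10% the one- to three-dose ratio is 1.4 to 3.0 for the pre-transplant sets and 5.3 to 18.3 for the total sets.

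**Number of people.** The expected number moved into the one-dose group is 28(w2 + w3)q. At q = 2% this is 0.17 to 0.37 for a pre-transplant count and 0.50 to 0.53 for a total count. At q = 10% it is 0.8 to 1.9 and 2.5 to 2.7.

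**Ordinary reactions.** With risk r per injection, independent across injections, the chance of any reaction in k windows is 1 − (1 − r)^k. At r = 10% this is 10%, 19% and 27% for k = 1, 2, 3; at r = 15% it is 15%, 28% and 39%. Both rates are illustrative.

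**Doses given after transplant.** Under Table 2 of Section 5.1, a participant with one pre-transplant dose can receive doses 2 and 3 after transplant. With strata defined by pre-transplant doses there are two ways to count. If all windows count, reactions to those later doses fall in the one-dose stratum. If only pre-transplant windows count, the 15/28/39% gradient returns and the post-transplant reactions are left out.

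**Participants never transplanted.** Section 4.4 expects that perhaps one-third of candidates may not be transplanted within the study period. Section 13.7 makes them evaluable for toxicity, while Section 1.3 frames the exploratory objectives among transplant recipients. They therefore either drop out of item 3 or have no value for its second stratifier.

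**Per-injection table, same model.** Events after dose 2 over participants given dose 2 is (w2 + w3)(1 − q)q / [(w2 + w3)(1 − q)] = q. The same holds at doses 1 and 3, so the ratio is 1.0 whatever the shares.

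**The case against.** The strongest reply is that item 3 most naturally means pre-transplant doses, as in the secondary endpoint and item 2c, and that this count is driven mainly by the date of surgery. Section 13.1 expects 24 to 28 of 96 to have a second dose before transplant, a one-dose share of 71% to 75% (13.3 uses the same 24 to 28 for a different quantity). At q = 2% the one-dose rate is then 0.02 / (0.75 + 0.25 × 0.02) = 2.6% to 0.02 / (0.708 + 0.292 × 0.02) = 2.8%, close to the true 2%. Qualifying events may also be rare: Section 6.2 reports 5 people with a vaccine-related serious event among 13,236, though that is a narrower category. The item is exploratory with no test, it does not rule out a per-injection table, and stratifying by dose number is a stated objective (1.3, 8.2).

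Most of this stands as a limit on size and on the remedy. It does not rescue the layout for reactions, because a pre-transplant count still leaves post-transplant reactions misplaced or omitted.

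The reply is also right that per-injection rates are not free of selection. If some people are more prone to react, 5.6 removes them before doses 2 and 3. The exposure problem is solved; that residual selection is not, and a list of stopped participants is needed beside the table.

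Stronger readings are tempting. A reader might infer that any reaction ends dosing. Section 5.6 does not say so: a grade 1 or 2 reaction without hypersensitivity does not trigger it. A reader might infer that only the one-dose group is loaded; the two-dose group is loaded in the same way. A reader might take rates such as 17% as what this trial will show; they need a total-dose reading and assumed shares.

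**Conclusion.** The concern holds in a limited form. Item 3 leaves the dose count undefined, and on either reading the table mixes three things when applied to vaccine reactions: stopping under 5.6, unequal numbers of 14-day windows, and doses given after transplant.

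The stopping artefact inflates the one- and two-dose groups, modestly under a pre-transplant count (ratio 1.4 to 3.0 in the sets tried) and strongly under a total count (5.3 to 18.3). The exposure artefact for ordinary reactions runs the opposite way, so no single direction of bias can be stated or corrected for by eye. These sizes rest on assumed per-dose risks and dose shares and on equal risk at each dose. With about 28 participants, stopping under 5.6 would move somewhere between none and three people into the one-dose group across the range tried. The exposure and post-transplant problems do not depend on rare events.

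The analysis is descriptive and exploratory, and the primary endpoint is unaffected. The change is worth making because it is nearly free. The documents do not support dropping stratification by dose number altogether.

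**What to change.** In Section 13.5, item 3:

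1. Make the main vaccine-reaction summary per injection: by dose number (1st, 2nd, 3rd) and by whether the injection was given before or after transplant, with injections given as the denominator and the 14-day window of 11.1.1. Include every vaccinated participant, as in 13.7, and say where injections in participants never transplanted are shown.
2. List the participants whose series was stopped under 5.6, with the dose and the event.
3. Keep the stated stratification by number of doses, specified as pre-transplant doses, for allograft rejection and opportunistic infections.
4. If reactions are also shown by number of doses, label that table as affected by 5.6 and by unequal exposure.

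The cost is a few lines of analysis-plan wording and a different table layout. Events are already to be collected after each dose, so no new data are needed. The objective and endpoint in 1.3 and 8.2 can stand, and no dosing rule changes.
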